13.2.1 Multi-Site Safety Monitoring

This is not a multi-site study.

13.3 Reporting Plans

Version number 1.8 and January 23, 2024

The Principal Investigator at BMC/BU Medical Campus will report Unanticipated Problems, safety monitors' reports, and Adverse Events to the BMC/BU Medical Center IRB in accordance with IRB policies:

- Unanticipated Problems will be reported to the BMC/BU Medical Campus IRB within 7 days of the investigator learning of the event.
- Adverse Events (including Serious Adverse Events) will be reported in summary at the time of
 continuing review, along with a statement that the pattern of adverse events, in total, does not
 suggest that the research places subjects or others at a greater risk of harm than was previously
 known.

13.4 Stopping Rules

The study has no pre-defined stopping rules since that devices are considered to be nonsignificant risk devices.

14 Data Handling and Record Keeping

14.1 Confidentiality

Subjects are assigned a code after consent and enrolled in the study. All coded records containing subject information will be stored in [name] offices under lock and key. Data will be kept in the [name] lab (M-1011). The door to the Vitamin D lab is accessed by those who have ID access to the lab. The data will be coded and after 7 years will be deidentified and kept indefinitely. Electronic information will be stored on a departmental server ("Y"drive), which is password protected. Paper records will be stored in a locked room for which only study staff will have access to. Master list will be stored on the Y drive and will not be stored with study data. All other electronic data will also be stored on the Y-drive which is password protected. Paper master list will be stored and locked in M1013; only study staff and study coordinator have access to this room. All locations where data will be kept are inaccessible to the public. Data will be available only to study personnel. Data will be kept in a locked room. Study code will be used for all study data that is collected. The study coordinator and study staff will keep the subject list on a secure network drive, which is password accessible only.

To maintain confidentiality for the zoom calls the zoom call will only be made at Boston University School of Medicine that is password protected or by zoom on a laptop computer that is connected to the VPN of Boston University School of Medicine.

14.2 Study Documentation, Source Data

Version number 1.8 and January 23, 2024

Data generated by the methods described in the protocol will be recorded. Data may be transcribed legibly for each subject or directly inputted into an electronic system or any combination thereof.

14.3 Study Records Retention

Study records will be retained for at least seven years after completion of the study. Documentation of informed consent of subjects will be retained for at least seven years after the study is closed, unless the IRB waived the requirement for informed consent or documentation of informed consent. Such records may be preserved in hardcopy, electronic or other media forms and must be accessible for inspection and copying by authorized individuals.

15 Statistical Plan

15.1 Study Hypotheses

We hypothesize that the wrist cooling device with a cooling porcelain plate more effective than the wrist cooling device with a fan only in reducing the severity of the hot flash.

15.2 Sample Size Determination

Reviewing the different types of treatment for hot flashes showed that the mean number of hot flashes per week decreased by 30%, 58%, 71% and 85% by Yoga poses, Citalopram, pregabalin and Gabapentin respectively. Also, hot flashes were reduced by 15-20% in the group receiving placebo.

We want to consider the sample size of a balanced, cross-over design and the within mean square error from the ANOVA table will be used to analyze crossover design.

We need 11 participants in each group to detect a 40% difference (average 60% reduction in severity in the treatment group and 20% reduction in severity in the placebo group) with 80% power using two-sided significance level of 0.05.

Therefore, with the expected 25% drop-out rate, we will recruit a total of 30 participants (15 per arm).

15.3 Statistical Methods

The ANOVA table for crossover design will be used for statistical analysis.

16 Ethics/Protection of Human Subjects

This study is to be conducted according to applicable US federal regulations and institutional policies (which are based in federal regulations, guidance, and ICH Good Clinical Practice guidelines).

Version number 1.8 and January 23, 2024

This protocol and any amendments will be submitted to the Boston Medical Center and Boston University Medical Campus IRB for formal approval of the study conduct. The decision of the IRB concerning the conduct of the study will be made in writing to the investigator.

All subjects for this study will be provided a consent form describing this study and providing sufficient information for subjects to make an informed decision about their participation in this study. The consent form will be submitted with the protocol for review and approval by the IRB. The consent of a subject, using the IRB-approved consent form, must be obtained before that subject is submitted to any study procedure. Consent will be documented as required by the IRB.

We will conduct a blinding index evaluation at the end of the study. This will be accomplished by standardized questionnaire that will be used to ask the subject about the use of the devices. The participants will be asked if they believe that they were assigned to the (i) control or (ii) treatment groups, or (iii) if they are uncertain of their assignment (the "don't know" response).

We will use a minor modified questionnaire published by

17 Literature References

- 1. Schrock NM et. al. pilot study to determine the effects of dronabinol on hot flash relief in breast cancer patients. Journal of Clinical Oncology, 22 (14): 8189, 2004.
- 2. Mao JJ et al. Electro Acupuncture versus gabapentin for hot flashes among breast cancer survivors: A randomized placebo-controlled trial. Journal of Clinical Oncology. 33 (31): 3615-3620; 2015
- 3. De Boer H. et al. Luteinizing hormone-releasing hormone and postmenopausal flushing. New England Journal of Medicine. 361: 1218-1219, 2009.
- 4. Guttuso T. Review of hot flashes diaries. Maturitas 71: 213-216; 2012

Version number 1.8 and January 23, 2024

18 Appendix

Schedule of Events

	Baseline	Week	Week	Week	Week	Week	Week	Week 7
		1	2	3	4	5	6	
	In-Person/ Virtually	At home					In-Person/	
					_			Virtually
Consent + HIPAA	Χ							
Authorization								
Eligibility	X							
Confirmation								
Receive Hot Flash	X							
Diaries and receive								
instruction how to								
use them								
Receive Two	X							
Devices	^							
and receive								
instruction how to								
use them								
Use of Hot Flash		Х	Х					
Diary								
Use of Hot Flash				Х	Х			
and Device A Diary								
Use of Hot Flash						Х	Х	
and Device B Diary								
Telephone/zoom			Х		Х		Х	
call								

Version number 1.8 and January 23, 2024

Intervention –		Х	Х			
Wear the first		^	,			
device						
Intervention –				Х	Х	
Wear the second				X		
device						
You will either						
return to see Dr.						
[name] or one of his						X
assistants to return						Χ
the devices and the						
diaries or send the						
devices and diaries						
to [name] or one						
of his assistants by						
FEDEX, UPS, USPS.						
You will then have						
the option to						
receive the						
commercially						
available wrist						
cooling device. You						
will also be asked						
questions about the						
use of the devices.						

Note: The subject will be allowed to monitor hot flash symptom without using the device for up to 4 weeks +3 days.

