The participants will be randomly assigned to wear one of the two wrist cooling devices that have an identical appearance during weeks 3 and 4 of the study and then use the other device during weeks 5 and 6 of the study. The devices will be attached to the wrist with the white plate placed on the interior side of the wrist. When activated, one device will turn on a cooling fan with the white plate being active and cooling the skin for up to 5 minutes, and the other device will turn on a cooling fan only for up to 5 minutes without the white plate being active to cool the skin. We will try to recruit 50% men and 50% women.

We will use a 3-category diary for hot flash symptom monitoring (assessed as mild, moderate, and severe). This study will take at least 6 weeks and up to 8 weeks requiring the participants to see a study team member either in person or virtually at the beginning and end of the study. The participants will receive three phone calls/ zoom calls during the study to remind them of when to use each device. The participant will be instructed that for the first 2 weeks that he /she will document as soon as possible in the Hot Flash Diary his/her daily each experience with hot flash and record the severity of each hot flash in the diary without using any device. They will then be instructed at the beginning of week 3 to use the device that they were randomly assigned to use. They can wear the device 24/7, i.e., all the time or they can place it on their wrist when they begin to experience a hot flash. They will be asked to fill in their Hot Flash and Device Use Diary as soon as possible after the hot flash the severity of each of their hot flashes that they experienced throughout the day and night. They will also be instructed at the time that they are documenting in the diary the severity of the hot flash as to whether or not they used the device while having the hot flash in the same

Version number 1.8 and January 23, 2024

diary. They will continue this activity for 2 weeks and then be instructed to use the second randomly assigned device at the beginning of week 5. They will use this device during weeks 5 and 6 of the study documenting as soon as possible in their diary the severity of each hot flash and whether or not they used the device during the hot flash.

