7.1 Subject Inclusion Criteria

In order to be eligible to participate in this study, an individual must meet all of the following criteria:

a. Experiencing at least 2 hot flashes per day that are either moderate and/or severe in intensity for at least the past 2 months.

Version number 1.8 and January 23, 2024

- Moderate hot flash: sensation of heat with sweating/dampness but able to continue activity with only brief fanning needed
- Severe hot flash: sensation of intense heat with sweating and causing disruption of current activity
- b. English speaking and English writing ability
- c. Must be 21 years old age or older

7.2 Subject Exclusion Criteria:

An adult who meets any of the following criteria will be excluded from participation in this study:

- 1. Temperature sensitivity due to cooling associated with an autoimmune or vascular disorder, such as Raynaud's phenomena, peripheral arterial disease or for any other reasons.
- 2. Any wrist skin sensitivity that is known to cause discomfort when any type of device such as a wristwatch is placed on the wrist.
- 3. Any lack of sensitivity to coolness on the wrists or hands
- 4. Current use of pharmaceuticals or devices to treat hot flashes.
- 5. Unable to understand and speak English and unable to write English

8 Study Intervention:

The subject will be randomized using the computer-generated randomization chart that will be produced by [name]. [name] will not be involved in any of the studies activities associated with interacting with this subject. The subject will be randomized in this double blinded randomized crossover study to use assigned device the depending upon their randomization during weeks 3 and 4 followed by using the other assigned device during weeks 5 and 6. For example, if the subject was randomized to use the device in box B for weeks 3 and 4 then they will be instructed to use the assigned device that in the box A for weeks 5 and 6 of the study. The wrist cooling device. The randomization chart will be given to [name] whose only activity is to keep the chart until the study is unblinded.

Wrist cooling device with a cooling porcelain plate

- The name of the device is Kulkuf
- Device size is 11.25 inches long and is 2.5 inches in width
- Device model is Kulkuf wrist cooling device. One of the devices when turned on will have the fan
 and wrist cooling porcelain plate activated while the other device that is identical in appearance

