The participant will be instructed that for the first 2 weeks that he/she will document in the diary labeled as Hot Flash diary each hot flash rating it as severe, moderate, or minimal without using the device. Study personnel will contact the participant by phone or zoom call 1-3 days before the expected date to start using the device that they were randomly assigned to use. During this call, they will be instructed at the beginning of week 3 to open up one of the two boxes (depending on which arm they are randomized into) that they were given during the first visit and begin using it. The device will be in the box with labeled instructions. They will be instructed that they can wear the device 24/7 i.e. all the time or they can place it on their wrist when they begin to experiencing a hot flash. The study personnel will also explain that during weeks 3 and 4 they will now be using the diary labeled as Hot Flash and Device Use. The study personnel will go over how to use this diary and how to record the severity of their hot flash and document whether or not they used the device.

If you are not available to use the device at the beginning of week 3, you will be allowed to keep documenting the severity of the hot flashes without using the device for another 2 weeks +3 days. You will be contacted by phone or zoom call again 1-3 days prior to the date you expect to start using the device.

At the end of week 4, they will be contacted again by the study personnel to stop using the current device and change to the second one that they were randomly assigned to use. They will continue to use the device and document the same information during weeks 5 and 6 of the study. Subjects who were seen in person will be instructed to return and see the PI or one of the study personnel after completing the activity and give the diaries and the devices to the PI or study personnel. Those subjects who are participating in the study virtually will be instructed to return and see the PI or one of the study personnel by zoom after completing the activity and return the diaries and the devices to the PI or study personnel by FEDEX, UPS or USPS. They will be asked questions about the use of the devices. During this in person or virtual visit, all participants will have the option to receive the commercially available wrist cooling device (valued at \$199), as compensation either in person or by FEDEX, UPS or USPS.

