In summary, there will be a total of two in-person visits for BUSM and local subjects and no in person visit for those are participating virtually 1.) During the first visit the subject will undergo consent process and randomization. Those subjects participating at BUSM or locally will receive the two devices and the diaries. Those subjects participating virtually will receive the two devices and diaries by FEDEX, UPS or USPS. They will be instructed how to use the diaries and the devices at the appropriate time. 2.) During the return visit at the end of the study the subject will be asked questions about the use of devices, and they will return the diaries and the devices either in person or by FEDEX, UPS or USPS. They will have the option to receive the commercially available cooling device as compensation for their participation in this study. There will be 3 telephone or zoom call visits including 1-3 days before the subject is scheduled/expected to use the assigned device during weeks 3 and 4 of the study and then a Zoom call our phone call 1-3 days before the subject is scheduled/expected to use the other device during weeks 5

Version number 1.8 and January 23, 2024

and 6 of the study. There may be multiple follow-ups calls if the subject is unable to start using the device on the indicated day. During week 6 before the end of the study they will get a reminder call to come back to return the diaries and the devices. The subjects in the virtual study will be reminded to send back the diaries and devices.

This is a double blinded crossover study; the devices will be in boxes that will be labeled as A or B. Only one co-investigator ([name]), who will not be communicating with the subjects will possess the information as to which one (A or B) of the labeled boxes that have a wrist cooling device that when turned on activates the fan and cooling porcelain plate or a wrist cooling device that when turned on only activates the fan. We will unblind the labels at the completion of the study for data analysis.

13 Assessment of Safety and Data Safety Monitoring Plan (DSMP)

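### The blinding question is described as an unanchored 'control' or 'treatment' guess, which has no single true value in a crossover where each completer uses both devices

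*Combined protocol and SAP*

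**What the plan says.** The blinding check is described at the end of Section 16 (Ethics/Protection of Human Subjects), outside the statistical plan. It is made once, at the end of the study, using a "standardized questionnaire that will be used to ask the subject about the use of the devices". On content, the plan says: "The participants will be asked if they believe that they were assigned to the (i) control or (ii) treatment groups", with a third option for those who are unsure. On origin, it says "We will use a minor modified questionnaire published by" and cites a post-trial survey from a long randomised trial in another disease area. Neither the items nor the modification are given. No index is named, and no rule says which answer is correct.

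The design is a two-period crossover. Under Section 2, participants wear one device in weeks 3 and 4 and "then use the other device during weeks 5 and 6 of the study". Section 8 gives the example "if the subject was randomized to use the device in box B for weeks 3 and 4", with box A to follow. Section 12 has participants "open up one of the two boxes (depending on which arm they are randomized into") at the start of week 3 and change to the other at the end of week 4. The labels are opened only at the end: "We will unblind the labels at the completion of the study for data analysis".

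Section 15.3 is one sentence on the crossover ANOVA and does not mention the index. Sections 4.2.1 to 4.2.3 do not list it as an outcome.

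**The concern.** The question as described suits a trial in which a participant belongs to one group throughout. Here randomisation sets only the order of the devices. For a completer, 'control' is true of one period and 'treatment' of the other. Without an anchor, the same answer can be scored right or wrong.

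This deserves attention because hot-flash severity is self-rated, and one device cools the skin while the other runs only a fan. Participants feel both, so they may well work out which is which. The end-of-study index is the only check the plan describes on its double-blind claim. If the guess is unanchored, a reassuring value could come from intact blinding or from participants who know exactly which device was which but answer about different ones.

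**Working it through.** **No figure to reproduce.** The plan gives no index value, formula or threshold. The number per order comes from Section 15.2: 11 per group, 25% drop-out, 30 recruited. This is consistent: 11/(1 - 0.25) = 14.7, so 15 per arm and 30 in total. In reverse, 30 × 0.75 = 22.5, or about 22 completers, 11 per order.

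**Assumptions.** The index is signed, b = (right - wrong)/n, with don't-know answers counted in n. Its 95% half-width is 1.96 × √{[(right + wrong)/n - b²]/n}. The plan does not name this index. All answer counts, don't-know shares and splits below are illustrations.

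**1. Dependence on the scoring period.** Suppose the cooling-first order gives 8 'treatment', 2 'control' and 1 don't know.
- Scored against the first device: (8 - 2)/11 = +0.55.
- Scored against the second device: (2 - 8)/11 = -0.55.
- Half-width either way: 1.96 × √[(10/11 - 0.545²)/11] = 0.46.

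**2. What an unanchored answer can still show.** Suppose the fan-first order gives the mirror image, 2/8/1. The 'treatment' share is then 8/11 against 2/11, a difference of 0.55, with two-sided Fisher p = 0.030. A difference between orders suggests unblinding whichever period is used for scoring.

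**3. What it can miss.** Suppose all 22 know which device is which, none answers don't know, and in each order 6 of 11 answer for the last device and 5 for the first.
- Cooling-first gives 5 'treatment' and 6 'control'; fan-first gives 6 and 5.
- Index against the last device, each order: (6 - 5)/11 = +0.09, half-width 1.96 × √[(1 - 0.0083)/11] = 0.59.
- Fisher between orders, 5/6 against 6/5: p = 1.0.

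A guess anchored to a stated device would give +1.0 for the same people.

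**4. How far that depends on the split.** Keep everyone unblinded but let 9 of 11 answer for the last device and 2 for the first.
- Index against the last device, each order: (9 - 2)/11 = +0.64, half-width 1.96 × √[(1 - 0.405)/11] = 0.46.
- Fisher between orders, 2/9 against 9/2: p = 0.009.

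Unblinding would be visible.

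**5. A different index.** On a James-type scale from 0 to 1 there is no sign, and random guessing sits at 0.5. If everyone is unblinded and answers about the second device, the value is 0 when scored against period 2 and 1 when scored against period 1. With an even split it is 0.5. The dependence on scoring and the masking both remain; only the labels change.

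**6. Precision with an anchored question.** At an index of 0 with n = 11, the half-width is 1.96 × √[(1 - d)/11], where d is the don't-know share. It is 0.59 for d = 0, 0.48 for d = 1/3 and 0.42 for d = 1/2.

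**The case against.** **The instrument is not visible.** Section 16 hands the items to a questionnaire about the devices, in the plural, and Section 12 and the Appendix also speak of questions about the devices. Section 16 gives the response options but does not say how often the question is asked. Section 15.2 uses treatment group and placebo group for the two device conditions of this same crossover, so 'group' in Section 16 may simply mean device condition, answered once per device. This stands as a limit. A reader might infer that the questionnaire itself is faulty, and the documents do not support that. What they do show is a description with no anchor and no scoring rule, and no other section supplies either.

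**Sign and 'near 0' presuppose a signed index.** This is correct, and they are stated here only under that assumption. The broader point, that the value turns on an unstated scoring choice, does not need it.

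**The masking example is close to a worst case.** Also correct. It needs a nearly even split, for which the documents give no evidence, and staff at the closing visit could clarify the question. The 9/2 case shows that unblinding need not be hidden.

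**A value near 0 would be weak evidence anyway.** With about 11 per order this is true under any wording. Anchoring removes the ambiguity but not the imprecision.

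**Little hangs on it.** The index is not a listed outcome, has no decision rule, and enters neither the ANOVA nor the sample size. That keeps the point minor.

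**Conclusion.** The point holds as a minor one about the plan's description. Followed as written, Section 16 yields a guess with no single true value for a completer, and its correctness depends on a choice the plan leaves open. Under a signed index with 11 per order, that choice moves the illustrative result from +0.55 to -0.55. Full unblinding could appear as +0.09 (half-width 0.59) with a 6/5 split, but would show as +0.64 (p = 0.009 between orders) with a 9/2 split.

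Two stronger readings are tempting. One is that the blinding check is worthless. It is not: a difference in answers between the two orders would still point to unblinding, although equal answers would not show that blinding held. The other is that the efficacy comparison is compromised. Nothing in the documents links the index to the primary ANOVA or the sample size, and the way the guess is worded says nothing about whether blinding will actually fail.

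The conclusion that the guess is unanchored rests on the text of Sections 2, 8, 12 and 16. The figures rest on the assumed index, completer numbers and answer patterns.

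**What to change.** In Section 16 and the existing end-of-study questionnaire:

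- **Anchor the guess by order of use**, for example: *The device I used first was: treatment / control / don't know.* This one item cures the defect. A second item for the second device is optional and largely its complement. If the questionnaire already asks per device, it is enough to say so in Section 16.
- **Avoid calendar weeks and box letters as anchors.** The Appendix lets the no-device period run to 4 weeks +3 days, so weeks vary between participants. The Appendix also puts a Device A diary in weeks 3 and 4, while the Section 8 example uses box B then.
- **Name the index and state the scoring**, including how don't-know answers count. After unblinding, score each guess against the device actually used in that period.
- **Report descriptively**, by device within period, with 95% intervals. If both items are asked, do not pool a participant's two guesses as independent.

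As a preference only, put the question before the closing-visit offer under which "all participants will have the option to receive the commercially available wrist cooling device".

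The cost is a questionnaire wording change and an IRB amendment, with no new visit, call or participants. There are three downsides. The first device is recalled 2 to 3 weeks after it was stopped (end of week 4 to the week 7 visit). A second guess may be inferred from the first. Half-widths of about 0.42 to 0.59 at an index of 0 mean that a value near 0 should not be presented as proof that blinding held.
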